8.2. MONITORING FOR ADVERSE EVENTS

All patients will daily self-monitor their parameters, AEs (if any) and concomitant medications (if any), and fill in an electronic study diary GENIUS ROSA. All patients may call the Investigator if needed.

During the study visit, the subject shall have the opportunity to spontaneously mention any problem and the investigator will search for possible adverse events by asking generic questions to the patient without pointing to specific events which may have occurred.

AEs should be reported for any clinically relevant change in concomitant condition(s) that is the result of an untoward (unfavorable and unintended) change in a subject's medical health. Changes in any protocol-specific systemic parameter evaluated during the study are to be reviewed by the Investigator. In addition, the subject's responses to any questionnaire utilized during the study are to be reviewed by the Investigator. Any untoward (unfavorable and unintended) change in a protocol-specific parameter or questionnaire response that is clinically relevant is to be reported as an AE. These clinically relevant changes will be reported regardless of causality.

8.3. RECORDING

AEs will be collected and recorded for any untoward event that occurs in a patient from the time he or she signs the ICF for the trial up to the end of the follow up period. Thus, any untoward medical occurrences or unfavorable and unintended signs, symptoms, or diseases that occur in the pretreatment, in treatment, or post treatment period are to be considered AEs and/or SAEs, and consequently recorded and reported as such. Should a non-serious AE become serious, the Investigator will then follow the same reporting procedures as for SAEs.

Each AE will be described by:

- Its duration (start and stop dates).
- Its seriousness.
- Its relationship to the study drug (suspected/unsuspected).
- Severity grade: The severity of AEs and SAEs will be graded using the Common Terminology Criteria for Adverse Events (CTCAE), version 5.0 (Appendix 3).
- Action(s) taken.
- Outcome.

Medical conditions/diseases and related signs/symptoms present before starting study treatment shall be documented in the medical history section of the eCRF; these conditions are considered AEs only if they increase either in frequency or severity once informed consent has been signed.

8.3.1. Relationship of AEs to the Investigational Product

The Investigator will assess the possible relationship between the AE and the investigational medication, according to the criteria in **Table** below:

Relationship of the Adverse Event to the IMP

None (Intercurrent Event)	An event that is not and cannot be related to the Investigational Product, e.g. patient is a passenger in a road traffic accident.
Unlikely (remote)	Relationship is not likely e.g. a clinical event including laboratory test abnormality with temporal relationship to drug administration which makes a causal relationship improbable and in which other drugs, chemicals or underlying disease provide more plausible explanations
Possible	Relationship may exist, but could have been produced by the patient's condition or treatment or other cause
Probable	Relationship is likely, the AE abates upon discontinuation of Investigational Product and cannot be due to the patient's condition
Highly Probable	Strong relationship, the event abates upon discontinuation of Investigational Product and, if applicable, re-appears upon repeat exposure

8.3.2. Severity of AEs

The Investigator will grade the severity of any AE using the classification according the CTCAE dictionary, as reported in Appendix 3.

The severity of AEs and SAEs will be graded using the CTCAE version 5.0. Any AE not listed in the CTCAE will be graded as follows:

Grade Definition:

1. Mild
2. Moderate
3. Severe
4. Life-threatening or disabling
5. Death.

8.3.3. Follow-Up of patients with Adverse Events

The Investigator is responsible for adequate and safe medical care of subjects during the trial and for ensuring that appropriate medical care and relevant follow-up procedures are maintained after the trial. All AEs should be followed-up to determine outcome of the reaction. The Investigator should follow up the event until resolution or stabilization of the condition. It is the Investigator's responsibility to ensure that the subjects experiencing AEs receive definite treatment for any AE, if required.

If subject was hospitalized due to a SAE, a copy of the discharge summary is to be forwarded to the Study Safety Contact as soon as it becomes available.

In addition, a letter from the Investigator that summarizes the events related to the case as well as results of any relevant laboratory tests also may be requested. Further, depending upon the nature of the SAE, Dompé may request copies of applicable segments of the patient's medical records. In case of death, a copy of the autopsy report, if performed, should also be provided.

The Investigator shall inform the Study Safety Contact with an appropriate written communication, whenever he becomes aware of new available information regarding the SAE, once the condition is resolved or stabilized and when no more information about the event is expected. Follow-up SAE information should be processed as initial SAE notification (see Par. 8.4.1).

For pharmacovigilance purposes, all SAEs should be followed-up in order to clarify as completely as possible their nature and/or causality and until all queries have been resolved. All SAEs will be followed up until the events resolve or the events or sequelae stabilize, or it is unlikely that any additional information can be obtained after demonstration of due diligence with follow-up efforts (i.e. subject or Investigator is unable to provide additional information, or the subject is lost to follow up), unless subject has withdrawn his/her consent.

8.4. SERIOUS ADVERSE EVENT REPORTING

8.4.1. Reporting Procedure for Investigators

The investigator must report all SAEs, regardless of presumed causal relationship to Study Safety Contact (i.e. Dompé Pharmacovigilance and Contract Research Organization Pharmacovigilance expert) recording the SAE data on the AEs section of the eCRF within 24 hours of learning of the event. The paper SAE forms are only intended as a back-up option when the eCRF system is not accessible. In this case, the original paper forms are to remain on site and copies are to be transmitted via email or confirmed facsimile (fax) transmission to:

- e-mail address: [contact]
- [contact]

Contact details for SAE reporting are provided in the section "Contact Information".

The investigator should also report information on SAEs that continue after patient has completed his/her participation in the study (whether study completion or withdrawal), unless patient has withdrawn his/her consent.

Information on SAEs will be recorded on the AEs section form in the eCRF. Follow-up reports (as many as required) should be completed following the same procedure; the system will mark the SAE form as "Follow up no. XX"

Whenever more than one SAE is observed, the Investigator should identify which is the primary adverse event, i.e. the most relevant one. If other events are listed in the same report, the Investigator, along with their relatedness to the Investigational Product, should identify which adverse events are serious and which are non-serious. In any case, the Investigator is requested to record his/her opinion about the relatedness of the observed event(s) with the investigational medication.

In line with CT3 Detailed Guidance and ICH E2A provisions, although the Investigator does not usually need to actively monitor patients for AEs once the trial has ended, if the Investigator becomes aware of

a SAE occurring to a patient after that patient has ended his/her participation in the study (whether study completion or withdrawal), the SAE should be reported by the Investigator using the following email address: [contact] or [contact]. Such “post-study cases” should be regarded for expedited reporting purposes by Dompé, as though they were study reports. Therefore, a causality assessment and determination of expectedness are needed for a decision on whether or not expedited reporting is required.

8.4.2. Adverse Events of Special Interest (AESI)

During the study all AESI will be considered equivalent to a SAE and will be reported following the procedures described above for the reporting of a SAE. The following events will be considered adverse events of special interest:

- Venous thromboembolic events (including deep vein thrombosis)
 - pulmonary embolism
 - retinal vein thrombosis
 - superficial vein thrombophlebitis
- Arterial thromboembolic reactions
- Thrombocytopenia

8.4.3. Conditions that should not be reported as serious adverse events

The conditions listed below, that may require hospitalization of a patient, are not considered to be SAE and shall not be reported as such, but only need to be recorded in the eCRF:

- Hospitalization for routine treatment or monitoring of the studied indication, not associated with any deterioration in condition.
- Trial end points
- Abnormal lab values or test results that do not induce clinical signs and/or symptoms and require intervention/therapy, i.e. are clinically significant.

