7. ENDPOINTS

7.1. STUDY ENDPOINTS

7.1.1. Primary endpoints

Virologic outcome. Proportion of participants with undetectable SARS-CoV-2 at PCR at day 7 after randomization.

Clinical outcome. Proportion of participants who not requires supplemental oxygen therapy (NEWS ≤ 2) and/or mechanical ventilation at day 14 after randomization.

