7.1.2. Secondary endpoints

- Proportion of participants with undetectable SARS-CoV-2 at PCR at day 14 after randomization at day 28 after randomization;
- Proportion of participants who does not require supplemental oxygen therapy (NEWS ≤ 2) and/or mechanical ventilation at day 7 and 28 after randomization;
- Proportion of patients in each NEWS category at time 7, 14 and 28 after randomization;
- Mean value of NEWS category at time 7, 14 and 28 after randomization;
- Proportion of participants with any adverse event with grade ≤ 2 according to CTCAE at day 7, 14 and 28 after randomization;
- Proportion of participants with any severe adverse events (grade ≥ 3 according to CTCAE) at day 7, 14 and 28 after randomization;
- Proportion of hospitalized participants who at the beginning of the study were at domicile isolation at day 7, 14 and 28 after randomization;
- Proportion of participants admitted to intensive care at day 7, 14 and 28 after randomization;
- Proportion of survivors at day 7, 14 and 28 after randomization;
- Mean variation of value of the following biomarker parameters, from base line to day 7, 14, 21 and 28 after randomization:
 - Complete blood cell counts;
 - Hepatic function (ALT, AST and bilirubin);
 - Coagulation (PT, aPTT and INR);
 - Other marker including (D-dimer, CPK, LDH);
- Quality of life questionnaire 3 months after the randomization.

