- is medically significant or important medical condition, i.e. an important medical event that based upon appropriate medical judgment, may jeopardize the patient and may require medical or surgical intervention to prevent one of the outcomes listed above.

An important medical condition is an event that may not result in death, be life-threatening, or require hospitalization but may be considered a SAE when, based upon appropriate medical judgment, it may jeopardize the patient and may require medical or surgical intervention to prevent one of the outcomes listed above. Examples of such medical events include allergic bronchospasm requiring intensive treatment in an emergency room or at home, blood dyscrasias or convulsions that do not result in patient hospitalization, or the development of drug dependency or drug abuse.

Pre-planned hospitalization or hospitalization for routine treatment or monitoring of the studied indication, not associated with any deterioration in condition are not considered to be SAEs (see Par. 8.3.2).

These events must be recorded in the AE page of the eCRF where a variable will be ticked to indicate that they are not SAEs.

Death shall always be reported as SAE and the cause of death shall always be specified when known. Death due to progression of disease may be unrelated to study treatment and causality shall be assessed by the Investigator. The investigator should report the event immediately to the sponsor and the sponsor shall comply with regulatory reporting, unless there is no reasonable possibility that the drug may have caused the fatal outcome of the disease progression.

Expectedness

Despite raloxifene has been on the market for many years with an authorised Summary of Product Characteristics, considering that this trial is investigating raloxifene in a new condition and patient population, all events (AE and SAE) will be assessed as unexpected by the Sponsor. The authorised SmPC may be considered the reference document for safety information, but shall not be used for the evaluation of the expectedness.

Suspected serious unexpected adverse reaction (SUSAR)

A suspected serious unexpected adverse reaction is defined as an adverse reaction that is both unexpected (not consistent with the applicable product information) and also meets the definition of a Serious Adverse Reaction.

Adverse event of special interest (AESI)

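### Protocol 8.4.3 exempts undefined trial end points from SAE reporting, which contradicts 8.1 and 8.4.1 for serious non-fatal endpoint events and 8.1 for death

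*Protocol*

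**What the plan says.** Protocol 8.4.3 introduces a list of conditions "that may require hospitalization of a patient" and says that they "are not considered to be SAE and shall not be reported as such, but only need to be recorded in the eCRF". The list includes "Trial end points" without further definition. The bullet before it carries a limit that the endpoint bullet lacks: "Hospitalization for routine treatment or monitoring of the studied indication, not associated with any deterioration in condition".

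The endpoints themselves are in Protocol 7.1. The clinical primary endpoint concerns "supplemental oxygen therapy (NEWS ≤ 2) and/or mechanical ventilation at day 14 after randomization". The secondary endpoints include "Proportion of hospitalized participants who at the beginning of the study were at domicile isolation", "Proportion of participants admitted to intensive care at day 7, 14 and 28 after randomization", survival, and adverse events of CTCAE grade 3 or higher.

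Protocol 8.1 makes inpatient hospitalisation, or its prolongation, a criterion for an SAE, and treats an event as serious when it is doubtful whether hospitalisation occurred. On death it says: "Death shall always be reported as SAE and the cause of death shall always be specified when known". Protocol 8.4.1 requires the investigator to report all SAEs within 24 hours, whatever the presumed cause. Protocol 8.4.2 treats every AESI (venous and arterial thromboembolic events, thrombocytopenia) as equivalent to an SAE. Protocol 8.4.4 requires any SUSAR to be submitted. None of 8.1, 8.4.1, 8.4.2 and 8.4.4 mentions an exception for trial endpoints.

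**The concern.** A patient admitted to hospital because COVID-19 has worsened has met a listed endpoint and also a seriousness criterion. Under 8.1 and 8.4.1 the site must report the admission within 24 hours. Under 8.4.3 it must not report it as an SAE. Sites that resolve the conflict differently will classify like events differently.

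Two features of this trial raise the stakes. First, 8.1 says that the sponsor will assess all events as unexpected, because the condition and population are new for raloxifene. Any serious event judged related is therefore a SUSAR, and the 7- and 15-day periods in 8.4.4 run from the sponsor's awareness. An event entered only as an endpoint, without the 24-hour notice, may not start that assessment on time. Second, the documents name no independent safety committee that would review exempt events. Section 8.4.4 describes periodic evaluation by the sponsor of the safety data it receives.

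There is also an analysis effect. SAP 15.1.2 counts treatment-emergent SAEs and non-serious events separately and has no rule for exempt endpoint events, so an event without the SAE flag moves from one count to the other.

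**Working it through.** The plan states no figure on this point. The check is a comparison of the text, followed by one calculation for scale.

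**Endpoint events against the reporting rules**

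| Endpoint event (Protocol 7.1) | Rule requiring a report | 8.4.3 read as written | Result |
|---|---|---|---|
| Hospitalisation with deterioration | 8.1 criterion, 8.4.1 | Exempt | Contradiction, no precedence stated |
| Intensive care admission | 8.1 (inpatient stay), 8.4.1 | Exempt | Contradiction, no precedence stated |
| Mechanical ventilation | 8.1 where a criterion is met, 8.4.1 | Exempt | Contradiction where serious |
| Grade 3 or higher adverse event | 8.1 only if a criterion is met | Exempt | Contradiction only where serious |
| Death | 8.1, always an SAE | Exempt | Contradiction, but 8.1 is explicit |
| Any of these when also an AESI | 8.4.2, equivalent to an SAE | Exempt | Contradiction, but 8.4.2 is explicit |

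The grade 3 row needs care. CTCAE grade is a severity scale (8.3.2), while seriousness is defined in 8.1. A grade 3 event is not an SAE by grade alone.

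**Does a narrower reading remove the conflict?** Suppose the bullet means only the two primary endpoints. Progression to oxygen or mechanical ventilation is still exempt. Suppose instead that it means disease-related efficacy outcomes. Admissions for deterioration are still exempt. The lead-in, which refers to conditions that may lead to hospitalisation, points at these same events. The conflict survives each reading.

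**Cross-reference.** For hospitalisations that are not SAEs, 8.1 refers the reader to Par. 8.3.2. That section covers severity grading; the exemptions are in 8.4.3.

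**Scale**

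- Inputs: Protocol 9.1 assumes that 50% on placebo and 75% on active treatment recover without oxygen or ventilation by day 14, so 50% and 25% need it. The planned interim is at 50 per arm. The expected total is 250 to 450. SAP 4.3 gives 68 patients included.
- Assumption: equal arms, with the 25% rate in both active arms.
- Formula: expected events = n per arm × (0.50 + 0.25 + 0.25) = n per arm × 1.00, which is one third of the total.
- Planned interim: 25 + 12.5 + 12.5 = 50 of 150.
- Expected range: 250/3 ≈ 83, to 450/3 = 150.
- Patients included: 68/3 ≈ 23.

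These are expected primary clinical endpoint events, not SAEs. Not every patient needing oxygen would meet an 8.1 criterion, and the documents do not give that share.

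**The case against.** A reader might infer that the events most important for safety would go unreported, that nearly every SAE is exempt, or that only death has an explicit rule to the contrary. The documents support none of these.

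- Death is always an SAE under 8.1, so for survival the fault is a contradiction and not an instruction left unopposed.
- All AESI are reported as SAEs under 8.4.2. These include venous thromboembolism, which Protocol 2.6.2 identifies as the only serious risk in the osteoporosis treatment population. An admission for pulmonary embolism has its own reporting rule.
- Exempting every endpoint would be self-defeating. Section 7.1.2 lists adverse events of grade 2 or lower as well as grade 3 or higher, so a wholly literal reading would leave the rest of section 8.4 almost nothing to report.
- The data are kept. Exempt events are recorded in the eCRF, with entry as soon as data are available (11.1), and each adverse event carries a relationship assessment (8.3). SAP 14.1.2 compares hospitalisation and intensive care admission with placebo and analyses survival; SAP 15.1.2 compares grade 3 or higher events. An undercounted SAE table would not hide those outcomes.
- The SUSAR duty in 8.4.4 has no endpoint exception.

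All of this stands, and it limits the point to non-fatal, non-AESI events that are serious and are also endpoints. It does not settle those events. For them, 8.4.3 says not to report, 8.1 and 8.4.1 say to report, and no text says which governs.

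**Conclusion.** The concern holds in limited form. For hospitalisation with deterioration, intensive care admission, mechanical ventilation and grade 3 or higher events that meet an 8.1 criterion, where non-fatal and not AESI, section 8.4.3 contradicts 8.1 and 8.4.1. For death it contradicts 8.1, although the 8.1 wording is plain enough that a report should follow.

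The potential loss is the SAE flag, the 24-hour notice that leads to SUSAR assessment, and a correct count of treatment-emergent SAEs. The underlying data and the comparisons between arms are not lost.

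The number of affected events cannot be computed. About 23 of 68 patients meeting the primary clinical event is a scale figure only; it rests on the planning rates and equal arms. The documents do not show that any event was in fact left unreported.

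This should be fixed, but the explicit rules for death and AESI and the eCRF record keep it short of a fault that invalidates the safety data.

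**What to change.** **Wording.** Reconcile 8.4.3 with 8.1, 8.4.1, 8.4.2 and 8.4.4. Either name exactly which endpoint events, if any, are exempt, or delete the bullet. State that the death, AESI and SUSAR rules and the 8.1 seriousness criteria prevail when an event is also an endpoint. Correct the 8.1 cross-reference to Par. 8.3.2.

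**Data.** SAP 4.3 records that enrolment stopped at 68 patients, so the most useful step now is a reconciliation before database lock. List all eCRF records of hospitalisation, intensive care admission, ventilation and grade 3 or higher events beside their SAE flags. Resolve each mismatch against 8.1, correct the treatment-emergent SAE tables, and complete any SUSAR assessment that was missed.

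**Cost.** A protocol change or site note and one listing. There will be some additional SAE reports. Because all events are assessed as unexpected, those judged related become SUSARs and may be unblinded by sponsor pharmacovigilance under 5.1.4 and 8.8. That should be weighed when deciding whether to name exempt events or delete the bullet.

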An adverse event of special interest (serious or non-serious) is an event thought to be [potentially] associated with the investigational compound or disease under study and for which close monitoring is advised. Reporting on Adverse Events of Special Interest is an emerging and ever more critical aspect related to characterizing the safety profile of a compound, for which ongoing monitoring and communication by the investigator to the sponsor as SAE is requested.

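### The laboratory bullet in Protocol 8.4.3 is defectively worded: read literally it removes clinically significant, treated abnormalities from SAE reporting, and on any reading it overlaps unresolved with the AESI rule in 8.4.2

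*Protocol*

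**What the plan says.** Protocol 8.4.3 introduces a list of conditions that may lead to hospitalisation and says that they "are not considered to be SAE and shall not be reported as such, but only need to be recorded in the eCRF". The third item on the list is "Abnormal lab values or test results that do not induce clinical signs and/or symptoms and require intervention/therapy, i.e. are clinically significant".

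Three other provisions bear on the same events:

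- **Protocol 8.1, seriousness.** Inpatient hospitalisation makes an event serious. So does an important medical event, described as one where, on medical judgment, "it may jeopardize the patient and may require medical or surgical intervention to prevent one of the outcomes listed above".
- **Protocol 8.1, AESI.** "An adverse event of special interest (serious or non-serious) is an event thought to be [potentially] associated with the investigational compound" or the disease under study. The investigator is asked to communicate such events to the sponsor as SAEs.
- **Protocol 8.4.2.** "During the study all AESI will be considered equivalent to a SAE and will be reported following the procedures described above" for SAEs. The list that follows includes "Thrombocytopenia", with no condition on symptoms, grade or treatment. SAP 15.1.2 repeats the list.

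No section states whether 8.4.2 or 8.4.3 prevails when both apply.

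**The concern.** An exemption of this kind should release sites from expediting trivial laboratory findings. Taken at its words, this one releases them from expediting the findings that need treatment, and it calls those findings clinically significant.

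The practical stake is the reporting clock. Protocol 8.4.1 requires SAEs to reach the sponsor within 24 hours. Under 8.1 the sponsor treats every event as unexpected, so any serious event judged related is a SUSAR, with the 7- or 15-day limit in 8.4.4. A site that relies on 8.4.3 and does not classify the event as serious may prevent that clock from starting. The same classification feeds the treatment-emergent SAE and serious adverse drug reaction outputs in SAP 15.1.2.

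Laboratory-only findings are foreseeable here. Protocol 6.2.2 schedules blood counts and hepatic tests at days 0, 7, 14, 21 and 28, and Protocol 2.5.3 lists thrombocytopenia among the known raloxifene reactions.

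**Working it through.** No arithmetic applies; this is a comparison of texts. The plan gives no figure to reproduce.

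**Step 1: how the bullet can be read.** Three readings are possible:

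- **A (literal):** the result causes no symptoms, and it does require therapy.
- **B (negated conjunction):** the result does not both cause symptoms and require therapy.
- **C (negation carried to both verbs):** the result neither causes symptoms nor requires therapy.

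| Laboratory result | A | B | C |
|---|---|---|---|
| No symptoms, no therapy | not exempt | exempt | exempt |
| No symptoms, therapy needed | **exempt** | **exempt** | not exempt |
| Symptoms, no therapy | not exempt | exempt | not exempt |
| Symptoms and therapy needed | not exempt | not exempt | not exempt |

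**Step 2: which reading the text supports.** C is probably what was meant. It requires the reader to supply a missing negation, because the closing gloss describes the exempted results as clinically significant. C also sits badly with the lead-in, since an insignificant value needing no therapy would hardly lead to hospitalisation. The literal reading fits both the gloss and the lead-in. The wording is therefore faulty whichever reading was intended.

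**Step 3: against 8.1.** Take an asymptomatic result that needs therapy (second row). If the patient is hospitalised, or if the important-medical-event test is met, 8.1 makes it an SAE. Under A or B, 8.4.3 says not to report it as one. Under C there is no conflict for this case. Not every result needing therapy meets an 8.1 criterion, so the conflict is confined to those that do.

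**Step 4: against 8.4.2, using thrombocytopenia without symptoms.**

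- Under A, the cases that need therapy are exempt by 8.4.3 and reportable by 8.4.2.
- Under B, all such cases are.
- Under C, the cases that need no therapy are.

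Some asymptomatic thrombocytopenia is covered by both sections on every reading. Correcting the negation alone therefore does not settle the overlap.

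**Step 5: events with no second route.** Liver-enzyme abnormalities are not on the AESI list. For them 8.4.2 offers no backstop, and only 8.1 stands against the literal wording of 8.4.3.

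**Step 6: what is still captured.** Protocol 6.2.4 has clinically relevant laboratory changes recorded as adverse events. Protocol 8.3 has seriousness, severity and relationship recorded for each. Protocol 8.4.3 itself keeps the eCRF entry. Protocol 9.5.4 and SAP 15.3 tabulate abnormal and clinically significant values and give shift tables. SAP 15.1.2 provides an AESI summary and listing that are not limited to serious events.

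**The case against.** The strongest case on the other side is that this is a drafting slip with a recognisable meaning. A sensible investigator would read the bullet as exempting results that neither cause symptoms nor need treatment, and under that reading an asymptomatic result needing therapy is not exempt. This stands to the extent that a reader who infers a deliberate instruction to withhold significant findings, or an exemption on every reading, goes beyond the text. It does not remove the point, because the sentence as printed does not say what was probably meant and the AESI overlap survives the charitable reading.

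A reader might also infer that asymptomatic thrombocytopenia goes unreported. The documents do not support that. AESI reporting under 8.1 and 8.4.2 does not depend on seriousness, so taking a result out of the SAE category does not clearly take it out of the AESI route. Protocol 8.4.4 also commits the sponsor to ongoing monitoring of AESIs. What remains is two instructions that pull in opposite directions with no order of precedence.

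A third tempting inference is that laboratory toxicity would be missed in the analysis. The recording and tabulation provisions rule that out.

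Nor can the problem be sized from the visit schedule. The four post-baseline draws give at most 4 x 68 = 272 scheduled draws for the enrolled patients, assuming full attendance. That counts occasions for a finding, not affected events.

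Finally, Protocol 2.5.3 says that the safety profile in COVID-19 is not known, but the same sentence anticipates no significant major risk. That bears on urgency and does not excuse conflicting reporting rules.

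**Conclusion.** The point holds as a drafting defect and an unresolved inconsistency in safety reporting. Literally applied, the third bullet of 8.4.3 contradicts 8.1 for asymptomatic laboratory abnormalities that need intervention and meet a seriousness criterion. On any reading it overlaps with the unconditional AESI rule in 8.4.2.

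The consequence is limited to SAE classification, 24-hour notification and SUSAR assessment for a narrow class of laboratory events, and to the serious-event tables that depend on the classification. Liver-enzyme abnormalities are the more exposed group because they have no AESI route. No size can be given, since the documents state no rate of laboratory abnormality or of intervention. The conclusion assumes that at least some sites would apply 8.4.3 as printed; nothing in the documents shows whether any did. Efficacy endpoints, sample size, power and alpha are not touched.

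**What to change.** Reconcile 8.4.3 with 8.1 and 8.4.2 in three steps:

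1. Reword the bullet so that it covers laboratory values or test results that neither cause clinical signs or symptoms nor call for intervention or therapy, and so are not clinically significant.
2. Add that the exemption never applies to an AESI under 8.4.2, or to any event meeting a seriousness criterion in 8.1. This is needed even if the first step is taken.
3. Check the laboratory adverse events already in the eCRF, platelets and liver enzymes in particular, for events not classified as SAE or AESI that should have been. SAP 4.3 records that enrolment stopped with 68 patients, so this retrospective check is likely to have more practical value than the amended text.

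The cost is about one sentence of protocol text, a site notice and a small data check, with possibly a few more reports to process.
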